14.1 BIOSTATISTICS

Phase I Component: The following design will be used to determine the maximum tolerated dose (MTD) of tretinoin in combination with decitabine. Three dose levels of tretinoin will be investigated (45 mg/m²/day, 65 mg/m²/day, and 85 mg/m²/day). Patients will be treated in cohorts of size three to six and the dosage will be escalated if the clinical toxicity is acceptable. Dose-limiting toxicity (DLT) is defined as a grade 3-4 non-hematologic toxicity observed within the first cycle of treatment. The design is constructed to reduce the chance of escalating the dose when the probability of DLT is high, and increase the chance of escalating the dose when the probability of DLT is low. The maximum tolerated dose is defined as the highest dose level with an observed incidence of DLT in no more than one out of six patients treated at a particular dose level. The dose escalation scheme is as follows:

Memorial Sloan Kettering Cancer Center
[name]
[name]

- 1) If none of initial three patients at a given dose level experience DLT, the next dose level is studied in another cohort of three patients.
- 2) If one of the initial three patients at a given dose level experience DLT, up to three additional patients will be treated at that same dose level. Escalation will continue if one of the six patients experience DLT.
- 3) If two or three patients experience DLT in the first three patients, or two or more patients experience DLT in six patients at a given dose level, the MTD will be determined as the preceding dose level.
- 4) If three or fewer patients are treated at a dose under consideration as the MTD, additional patients to total six will be treated at that level to confirm MTD

The dose escalation scheme provides the following probabilities of escalation based on the true chances of DLT at a specific dose level. One can see that the probability of escalation is high if the toxicity risks are low.

True Probability of Toxicity:	.10	.20	.30	.40	.50	.60
Probability of Escalation:	.91	.71	.49	.31	.17	.08

If 2 patients experience DLT at the first dose level (45 mg/m²/day), a dose de-escalation scheme will be employed, testing doses of 30 mg/m²/day and 15 mg/m²/day. Cohorts of three to six patients will be treated at each dose level, if necessary.

A minimum of two and a maximum of 18 patients could be treated in this portion of the trial. At the end of this study, the phase II component of the trial will begin at the MTD determined. The six patients treated at the MTD will be included as part of the phase II component of the trial.

Phase II Component: The primary objective of the phase II component of the trial is to determine the response rate (defined as Complete Remission or Partial Remission) to the combination of decitabine and tretinoin (with tretinoin administered at the MTD from the phase I component above) in patients with myelodysplastic syndromes. A Simon minimax two-stage design will be utilized, in which a 10% response rate is considered not promising, a 25% response rate is considered promising, and the probabilities of a type I error (falsely accepting a non-promising therapy) and type II error (falsely rejecting a promising therapy) are set at 0.10 and 0.10, respectively.

In the first stage of this design, 27 patients will be accrued. If at least 3 patients achieve a complete remission or partial remission among these 27 patients, then an additional 13 patients will be accrued to the second stage. If two or fewer responses are seen, the study will be terminated and declared negative. At the end of the trial, the combination will be considered

worthy of further study if 7 or more responses are observed out of 40 patients. This design yields at least a 0.90 probability of a positive result if the true response rate is at least 25% and yields a 0.90 probability of a negative result if the true response rate is 10%.

Additionally, secondary objectives will be examined in patients enrolled into phase I and phase II components of the trial. The proportion of Hematologic Improvements will be recorded. The frequency of transfusions, bleeding and infections will be summarized. Peripheral blood and bone marrow aspirate mononuclear cells will be assessed for the extent of DNA methylation using PCR based technologies. The expression and methylation status of specific genes will be analyzed, focusing on, but not necessarily restricted to the following genes: p57, p 21, p73, p15INK4b, TGF β RII, RAR β , and JunB. In this study we will examine whether methylation of these genes (yes/no) as well as flow cytometric indicators of differentiation and apoptosis, correlate with response to treatment. Associations will be examined using a Fishers exact test. These analyses are exploratory and hypothesis-generating.

In addition, bone marrow and blood mononuclear cells will be analyzed using gene profiling (Affymetrix). In order to attempt to identify genes that are most affected by treatment, a paired sample t-test will be used to rank the genes. Samples pre and post chemotherapy will be paired together and a fold change will be computed for each pair. The log of the fold change will then be used and genes will be scored by how large and consistent the fold change is among the patients. To deal with issues of non-normality of the signal levels p-values will be computed using a permutation algorithm which shuffles the sample labels and recomputes the t-score. To correct for multiple testing the False Discovery Rate (FDR) method will be used to compute rate of false positives. Due to the two-stage design, and uncertainty regarding the rate of disease response, the exact number of samples that will be included in the microarray analysis is unknown.

Frequencies of toxicities based on the NCI Common Toxicity Criteria version 2.0 will be tabulated.

A minimum of 27 patients (including 6 patients from the phase I component) and a maximum of 40 patients will be accrued to the phase II component of this trial. Approximately 3-4 patients will be accrued per month, and hence, the trial will be completed in approximately 2 years.

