In three European multi-center, phase II trials and one MSKCC phase II trial, decitabine was given to 177 elderly patients (median age 70) at a dose of 45-50 mg/m²/day for three days every 6-8 weeks. Across those studies, the overall response rate was 49%, including a CR rate of 24%. The median response duration was 9 months (19). Decitabine was subsequently compared to supportive care in a multi-center, randomized, phase III trial in North America (20). In the phase III trial, decitabine was given as an inpatient, 15 mg/m² IV every eight hours for 9 consecutive doses (135 mg/m²/cycle) every 6 weeks, which was the same dose and schedule given to the majority of the decitabine phase II participants. The overall response rate (CR + PR) was (15%) compared with a 0% ORR in the supportive care arm, with an 8% CR rate (IWG Response Criteria). The median time to death or AML progression (composite endpoint) overall was 491 days vs. 274 days, and survival was prolonged in responders (657 days) compared to non-responders (384 days). Patients with IPSS High-Risk disease and Intermediate-2 Risk were shown to have a statistically significant prolongation in the time to AML progression or death (12 months vs. 6.8 months, p = .03), the primary endpoint of this phase III trial. The difference was even greater when IPSS High-Risk cohort was analyzed and the treatment arm was compared to supportive care (time to AML progression or death 9.3 months vs. 2.8 months, p = .01). In another sub-group analysis, clinical response (PR + CR), a secondary endpoint, was significantly improved for the Intermediate-2 Risk group (21% vs. 0%, p = .005). The response rate for IPSS High-Risk patients was 13% (p = .234).

In a more recent three-arm, phase II study, 100 mg/ m² decitabine was given every 4 weeks using three different outpatient schedules: 1) 20 mg/m²/day intravenously for 5 consecutive days; 2) 10 mg/m² per day for ten days; 3) 20 mg/m² subcutaneously for five days (21). The 5-day intravenous schedule produced a complete response rate (modified IWG criteria) of 40%, which represents a potential substantial improvement in the response rate seen for the three day schedule used previously in the bulk of the phase II studies and in the randomized phase III trial.

All-Trans Retinoic Acid (Tretinoin)

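### Does an unsourced 10% null, set below the response rates cited for decitabine alone, undermine the phase II decision rule?

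*Combined protocol and SAP*

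**What the plan says.** Section 14.1 gives the phase II primary objective as "to determine the response rate (defined as Complete Remission or Partial Remission") for decitabine plus tretinoin at its MTD. The design is a Simon minimax two-stage design "in which a 10% response rate is considered not promising, a 25% response rate is considered promising", with type I and type II errors of 0.10 each. The trial stops at two or fewer responses in 27 patients. Otherwise 13 more are enrolled, and the combination is "worthy of further study if 7 or more responses are observed out of 40 patients". No reason is given for 10% or 25%, and no interval for the response rate is specified.

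Section 3.0 reports these results for decitabine alone:

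- Phase III, three-day schedule: "The overall response rate (CR + PR) was (15%) compared with a 0% ORR in the supportive care arm". In subgroups, response "was significantly improved for the Intermediate-2 Risk group (21% vs. 0%, p = .005"), and "The response rate for IPSS High-Risk patients was 13% (p = .234").
- Pooled phase II, three-day dosing: "the overall response rate was 49%, including a CR rate of 24" per cent.
- The five-day schedule used in this trial: "The 5-day intravenous schedule produced a complete response rate (modified IWG criteria) of 40" per cent.

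Sections 4.3 and 17.1 give as rationale that tretinoin may raise the response rate above that of decitabine alone. Section 6.2 admits patients previously treated with 5-azacytidine, whatever their response, and patients who responded to decitabine and progressed after stopping it.

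**The concern.** One component of the combination is already known to be active, and every overall response rate cited for it exceeds the null. Only the 8% phase III rate is lower, and that is CR alone. A combination no better than its backbone could therefore pass the test quite often.

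The bar for success, 7 of 40 or 17.5%, is only 2.5 percentage points above the cited 15%. It is far below the 40% CR quoted for the same decitabine schedule. A reader who takes the rationale in Sections 4.3 and 17.1 at face value could read a positive trial as evidence that tretinoin helps. With no planned interval and no stated basis for the null, nothing in Section 14.1 warns against that reading.

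**Working it through.** **Inputs.** From Section 14.1: p0 = 0.10, p1 = 0.25, errors 0.10 and 0.10, 27 then 13 patients, continue at 3 or more of 27, positive at 7 or more of 40. From Section 3.0: 13%, 15%, 21% and 40% as reference rates.

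**Step 1: reproduce the design.** For a true rate p,

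P(positive | p) = Σ over x = 3 to 27 of C(27, x) p^x (1 − p)^(27 − x) × P[Bin(13, p) ≥ 7 − x].

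- p = 0.10: 0.0977, so a negative result has probability 1 − 0.0977 = 0.902.
- p = 0.25: 0.9001.

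A search for the smallest total size that meets both error limits returns the same design (27 and 40 patients, boundaries 2 and 6). The plan's figures are right. The probability falls as p falls, so 0.10 bounds the error for every true rate at or below 10%: it is 0.037 at 8% and 0.003 at 5%.

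**Step 2: apply the rule at the cited rates.**

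| True CR+PR rate | P(positive) | P(stop at stage 1) |
|---|---|---|
| 13% | 0.255 | 0.300 |
| 15% | 0.388 | 0.207 |
| 21% | 0.759 | 0.057 |
| 40% | 0.999 | 0.0002 |

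So a positive result does not by itself separate the combination from decitabine alone.

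**Step 3: see what each result excludes.** The one-sided 90% lower limit (Clopper-Pearson) is the p that solves P[Bin(40, p) ≥ x] = 0.10. The version allowing for two-stage sampling solves P(continue and total ≥ x | p) = 0.10.

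| Responses of 40 | Lower limit | Two-stage version | Two-sided 95% interval |
|---|---|---|---|
| 7 | 10.0% | 10.1% | 7.3% to 32.8% |
| 8 | 12.0% | 12.0% | 9.1% to 35.7% |
| 9 | 14.1% | 14.1% | 10.8% to 38.5% |
| 10 | 16.2% | 16.2% | 12.7% to 41.2% |

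Results of 7 to 9 do not exclude 15%, and 10 or more do. At a true 15%, P(10 or more) is 0.067, so 0.388 − 0.067 = 0.321 of the 0.388 (83%) comes from 7 to 9 responses. At the design target of 25%, P(10 or more) is 0.560, and 0.560 / 0.900 = 62% of positive trials would exclude 15%. The interval separates the two situations and needs only the response count and the number treated.

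**Step 4: price a higher null.**

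- Same 27 + 13 patients, stop at 3 or fewer of 27, positive at 10 or more of 40: type I error 0.067 at 15% and power 0.80 at an assumed 30%, but power at the stated 25% falls from 0.90 to 0.56.
- Minimax design for an assumed 15% against 30% with errors 0.10 and 0.10: 34 + 19 = 53 patients, 53 − 40 = 13 more than planned. At the stated accrual of 3 to 4 a month that is 13/4 to 13/3, or about 3 to 4 extra months.

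**The case for a change.** The strongest case for a change is that the protocol motivates the trial by improvement over decitabine, cites decitabine rates from 13% to 49%, and then tests against 10% without explanation. An objective worded as determining a response rate calls for an estimate with its precision, and the plan does not commit to one. The remedy would cost only a few sentences.

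The facts stand: no source, no planned interval, and a probability of 0.39 at 15%. Several things limit what follows from them.

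- The 0.39 is not a type I error. Section 14.1 asks whether the combination's own response rate is promising, Section 4.2 calls the efficacy aim preliminary, and the positive verdict is only that more study is merited. Asking the plan to disown a comparative claim asks it to deny something its analysis section never asserts.
- The higher benchmarks are weak. The 40% is CR only, under modified criteria, from a study that Section 17.1 calls small. Section 3.0 does not say which categories make up the 49%. The 15% is the one whole-trial figure on the trial's endpoint, and it comes from another schedule.
- Section 6.2 admits pretreated patients, for whom a lower reference rate is plausible. The documents give no response rate for such patients, so this can be neither sized nor ruled out. It is reason enough not to call 10% wrong.

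**Conclusion.** No change to the plan is needed. The missing interval is a gap that any competent analyst fills: an exact interval, preferably allowing for the two-stage sampling and reported also after a stop at 27, comes straight from the response counts. The sampling adjustment moves only the limit at 7 of 40, from 10.0% to 10.1%. The missing source for 10% and 25% is a matter of documentation; supplying it would alter no boundary, sample size or decision. The one substantive alternative, a higher null, is a fair trade-off: it costs either power at 25% (0.90 to 0.56) or 13 more patients.

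What remains is a point of interpretation. Seven to nine responses in 40 would show activity above 10% without excluding the cited 15%, while ten or more would exclude it at one-sided 0.10. Even then the comparison is with another trial's schedule and patients. This conclusion takes 15% as the relevant decitabine-alone rate, treats responses as independent with a common probability, and reads Section 14.1 as a screen for activity.

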Treatment will be recycled every 4 weeks, provided there is adequate recovery from non-hematologic toxicities. The effects of decitabine and escalating doses of tretinoiin on markers of differentiation and apoptosis, and on expression of key genes will be assessed.

FIGURE 1.1: Study Design

Memorial Sloan Kettering Cancer Center
[name]
[name]

	Treatment Period →								
	Cycle # 1 →				Cycle #2, #3, #4, etc. →				End of Study
Decitabine	X				X				
Tretinoin			X				X		
Treatment Days (D)	D1 - D5	D 6 - D 9	D10 - D19	D 20 - D 28	D 1 - D 5	D 6 - D 9	D 10 - D 19	D 20 - D 28	Day X

Patients will receive treatment for a minimum of 4 cycles, barring removal for progression of disease or excessive toxicity. Patients must achieve hematologic improvement (HI) or Bone Marrow PR/CR by the completion of cycle #6. Patients achieving HI or bone marrow PR/CR by the completion of cycle #6 may receive up to a total of 10 cycles of therapy, barring excessive toxicity. If the best response after cycle #6 is Stable Disease, these patients will be removed from study. Patients in the phase I study will continue at the study entry dose. Treatment will be interrupted for grade III or IV non-hematologic toxicity attributable to tretinoin or decitabine. Therapy may be resumed with the next cycle of treatment as long as the toxicity has decreased to < grade 2 within 8 weeks of the last treatment administration. However, these patients will receive a 25% dose reduction in tretinoin or decitabine (which ever treatment is suspected or both if the attribution is unknown) when treatment resumes. All patients will be followed for Serious Adverse Events (SAEs) for 30 days after the completion of the last cycle of therapy (each cycle is 4 weeks).

TIME TO COMPLETION: It is anticipated the study will complete accrual in 18–24 months.

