2.0 OBJECTIVES AND SCIENTIFIC AIMS

Primary Endpoint:

Phase I: Define the hematologic and non-hematologic toxicities of combining a hypomethylating agent (Decitabine, DAC) with escalating doses of the transcriptional modifying agent tretinoin (All Trans Retinoic Acid), and define the MTD of tretinoin in combination with decitabine.

Phase II: Determine the clinical remission rate (rate of Complete Remission, Partial Remission) of the combination of decitabine and tretinoin in patients with myelodysplastic syndromes, and determine the rate of Hematologic Improvement.

Secondary Endpoints (Phase I and Phase II):

1. Evaluate the ability of decitabine and tretinoin to affect bone marrow function by monitoring frequency of transfusions, frequency of bleeding and infection, and changes in bone marrow morphology and cytogenetics.
2. Evaluate differentiation (using morphology and flow cytometry) and apoptosis (using flow cytometry) induced by treatment with decitabine and tretinoin.
3. Perform gene profiling studies to determine if gene expression changes are induced by decitabine and tretinoin.
4. Evaluate the ability of decitabine and tretinoin to cause demethylation of specific genes.
5. Correlate clinical response with gene expression, demethylation of specific genes, and flow cytometric indicators of differentiation and apoptosis.

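### Hematologic Improvement shares the phase II primary endpoint with CR/PR, yet section 14.1 examines it in all phase I and phase II patients without a dose split, so its rate would not be the rate at the phase II dose

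*Combined protocol and SAP*

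**What the plan says.** Under the phase II primary endpoint, section 2.0 names the CR/PR rate "and determine the rate of Hematologic Improvement". The same section heads its five secondary items "Secondary Endpoints (Phase I and Phase II"), and HI is not one of them.

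Section 14.1 defines the phase II primary objective as CR or PR alone, with tretinoin at the MTD. Of the phase I patients, only those at the MTD are carried over: "The six patients treated at the MTD will be included as part of the phase II component of the trial". It then says: "Additionally, secondary objectives will be examined in patients enrolled into phase I and phase II components of the trial". HI comes directly after that sentence: "The proportion of Hematologic Improvements will be recorded". The frequencies of transfusions, bleeding and infections follow, then the marker analyses. None of these has a dose stratum, a dose term or a restriction to the MTD.

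On dose and markers, section 1.0 says: "The effects of decitabine and escalating doses of tretinoiin on markers of differentiation and apoptosis, and on expression of key genes will be assessed". The marker analyses in section 14.1 are Fisher tests of marker against response and a paired ranking of genes before and after treatment. Neither uses dose.

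**The concern.** Two rates that section 2.0 puts side by side would be estimated in different sets of patients. CR/PR describes the regimen taken forward. HI would describe that regimen mixed with whichever tretinoin doses were tried and not selected. Section 9.0 keeps phase I patients at their entry dose, so by design the non-MTD patients do not move to the MTD.

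A reader of the results would naturally set the HI rate beside the CR/PR rate, or add the two, as if both applied to the phase II dose. The same holds for the transfusion, bleeding and infection frequencies. Separately, the summary promises a look at marker effects across escalating doses, and the statistical section has no analysis that delivers it.

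**Working it through.** **1. The plan's own figure.** Section 14.1 gives 27 then 13 patients, continuing with 3 or more responses, and positive with 7 or more of 40. P(positive) is the sum over x from 3 to 27 of P(Bin(27, p) = x) × P(Bin(13, p) ≥ 7 − x).

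- p = 0.25: 0.9001 (stated: at least 0.90).
- p = 0.10: 0.0977, so P(negative) = 0.902 (stated: 0.90).

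The design reproduces. It counts only CR/PR in MTD patients, so the HI analysis set cannot alter it.

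**2. How many patients are at a non-MTD dose.** Inputs are the rules in sections 9.0 and 14.1: cohorts of 3 to 6; levels 45, 65 and 85 mg/m²/day, with 30 and 15 if de-escalated; and six patients at the MTD. A level that was passed holds 3 or 6 patients. A level that failed holds 2 to 6, the lower figure applying if a cohort stops at its second DLT, in line with the stated phase I minimum of two.

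| MTD (mg/m²/day) | Other levels used | Non-MTD patients |
|---|---|---|
| 85 | 45 and 65, both passed | 6 to 12 |
| 65 | 45 passed, 85 failed | 5 to 12 |
| 45 | 65 failed | 2 to 6 |
| 30 | 45 failed | 2 to 6 |
| 15 | 45 and 30, both failed | 4 to 12 |

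The upper limit agrees with the stated phase I maximum: 18 − 6 = 12.

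**3. Share of the combined set.** With n patients at the MTD (27 or 40) and h at other doses, the share is h/(n + h).

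- MTD 85, full trial: 6/46 = 13% to 12/52 = 23%.
- MTD 85, stopped after stage 1: 6/33 = 18% to 12/39 = 31%.
- All paths: 2/42 = 5% to 12/39 = 31%. Between 69% and 95% of the set is therefore at the MTD.

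**4. Effect on the HI rate.** The shift from the MTD rate is −(h/(n + h)) × (HI at MTD − HI at other doses). The documents give no HI rates by tretinoin dose, so these are assumptions: 40% at the MTD, and 20% or 30% elsewhere.

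| n + h | Pooled HI, 20% elsewhere | Shift (points) | Shift, 30% elsewhere (points) |
|---|---|---|---|
| 27 + 12 | 33.8% | −6.2 | −3.1 |
| 40 + 12 | 35.4% | −4.6 | −2.3 |
| 40 + 6 | 37.4% | −2.6 | −1.3 |
| 40 + 2 | 39.0% | −1.0 | −0.5 |

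For scale, the exact 95% interval for 16/40 is 25% to 57%.

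**5. What a by-dose table can carry.** With 2 to 6 patients per non-MTD level, the exact 95% interval is 1% to 91% for 1/3 and 4% to 78% for 2/6. Such a table can only describe.

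**The case against.** The best defence is that examining secondary objectives in both phases is deliberate, agrees with the heading in section 2.0, and does not exclude summaries by dose. That is fair: one merged estimate is the natural reading of section 14.1, not its explicit words. The defence does not cover HI, however, because section 2.0 lists HI under the phase II primary endpoint and not under that heading.

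The defence can add that sampling error exceeds the bias. Step 4 supports this. It limits how much the point matters, but does not settle which patients the HI rate refers to.

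A reader might also infer more than the documents support:

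- **That the pool could span 15 to 85 mg/m²/day.** Under sections 9.0 and 14.1 a trial either escalates (45 to 85) or de-escalates (45 to 15), not both.
- **That the escalating-dose aim is never analysed.** The formal objective with those words is the phase I one ("Define the hematologic and non-hematologic toxicities of combining a hypomethylating agent (Decitabine, DAC) with escalating doses of the transcriptional modifying agent tretinoin"), and the DLT and MTD rules evaluate DLTs by dose level. Only the marker part lacks an analysis. That part is worded this way in section 1.0 alone; section 9.0 states the marker aim without mentioning escalating doses.
- **That the trial discards its only contrast on what tretinoin adds.** Section 10.4 and Appendix IV schedule samples on day 10, before tretinoin, and on day 19, after it. That is a within-patient contrast.
- **That dose mixing would seriously mislead the marker-response tests.** Take 40 MTD and 12 lower-dose patients, marker change of 60% and 20%, response of 25% and 5%, and no association within dose (all assumed). The expected pooled table is 6.12, 20.28, 4.48, 21.12, so the odds ratio is (6.12 × 21.12)/(20.28 × 4.48) = 1.42. In simulation, Fisher's test at 0.05 rejects about 5% of the time. Section 3.0 cites 15% CR + PR for decitabine alone in its phase III trial; with 15% at lower doses the odds ratio falls to 1.18. Section 14.1 already labels these tests exploratory.

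**Conclusion.** The point holds for HI and the clinical frequencies reported with it. Sections 2.0 and 14.1 disagree on the status of HI, and the set named in section 14.1 gives it a different denominator and dose mix from CR/PR. Some mixing is certain in any trial that reaches phase II: 2 to 12 patients, or 5% to 31% of the combined set.

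The likely distortion is modest: about 1 to 6 points under the assumed 40% and 20%, and half that with 30% at other doses. These figures assume that HI differs by tretinoin dose, which the documents neither state nor rule out. The CR/PR decision rule and its error rates stand. The missing by-dose marker summary is a smaller gap between sections 1.0 and 14.1.

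**What to change.** 1. Reconcile sections 2.0 and 14.1 on whether HI is part of the phase II primary endpoint or a secondary one.
2. Estimate HI and the transfusion, bleeding and infection frequencies in the same set as CR/PR: patients assigned to tretinoin at the MTD, including the six carried over from phase I. List patients at other dose levels separately.
3. Add a table by assigned tretinoin dose level of the day 10 to day 19 marker change, labelled descriptive, with no formal trend claim.
4. Keep the marker-response Fisher tests exploratory in both phases, and show the MTD-only result alongside.

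The cost is a few sentences in section 14.1 and some extra table columns. No new patients or samples are needed. The HI interval becomes slightly wider, resting on up to 40 rather than up to 52 patients: by the square-root rule, √(52/40) = 1.14, about 14% wider at the same rate.

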11.5 Establishment of Maximum Tolerated Dose (MTD)

In the phase I portion of this study, the MTD of tretinoin will be determined (within the range of 15 mg/m² - 85 mg/m²) when given in combination with decitabine. At least three patients will be treated at each dose level, starting with 45 mg/m²/day, which is 30% of the MTD (in a phase I MTD of tretinoin monotherapy in MDS patients, the MTD was 150 mg/m²/day when given daily for 6 weeks (34)). Additional dose levels will be tested as follows: 65 mg/m²/day and 85 mg/m²/day.

A dose-limiting toxicity is defined as a grade III or IV non-hematologic toxicity (NCI CTC, ver. 2.0). If at any dose level one patient experiences grade III or IV non-hematologic toxicity (according to the NCI CTC version 2.0) attributable to tretinoin, three additional patients will be added to that dose level. If a second patient experiences grade III or IV non-hematologic toxicity, the dose level below will be considered the MTD, which is defined as the dose level below that which produces Grade III/IV non-hematologic toxicity in $\geq 33\%$ of patients.

If a DLT is experienced at 45 mg/m²/day and is attributable to tretinoin, a dose de-escalation schema will be employed (see section 9.0) to determine the MTD below 45 mg/m²/day.

If no DLT is seen after the 85 mg/m²/day dose level is complete, the phase II portion will proceed using tretinoin at a dose of 85 mg/m²/day. However, once the MTD is established, a total of 6 patients will be treated at that level to confirm the MTD before proceeding to the phase II portion of the study.

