16.3 Data and Safety Monitoring

The Data and Safety Monitoring (DSM) Plans at Memorial Sloan-Kettering Cancer Center were approved by the National Cancer Institute in September 2001. The plans address the new

Memorial Sloan Kettering Cancer Center
[name]
[name]

policies set forth by the NCI in the document entitled “Policy of the National Cancer Institute for Data and Safety Monitoring of Clinical Trials” which can be found at:

<http://cancertrials.nci.nih.gov/researchers/dsm/index.html>. The DSM Plans at MSKCC were established and are monitored by the Office of Clinical Research. The MSKCC Data and Safety Monitoring Plans can be found on the MSKCC Intranet at:
<http://mskweb2.mskcc.org/irb/index.htm>

There are several different mechanisms by which clinical trials are monitored for data, safety and quality. There are institutional processes in place for quality assurance (e.g., protocol monitoring, compliance and data verification audits, therapeutic response, and staff education on clinical research QA) and departmental procedures for quality control, plus there are two institutional committees that are responsible for monitoring the activities of our clinical trials programs. The committees: *Data and Safety Monitoring Committee (DSMC)* for Phase I and II clinical trials, and the *Data and Safety Monitoring Board (DSMB)* for Phase III clinical trials, report to the Center’s Research Council and Institutional Review Board.

During the protocol development and review process, each protocol will be assessed for its level of risk and degree of monitoring required. Every type of protocol (e.g., NIH sponsored, in-house sponsored, industrial sponsored, NCI cooperative group, etc.) will be addressed and the monitoring procedures will be established at the time of protocol activation.

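### Phase II has no stated trial-level toxicity pausing criterion, although up to 34 further patients are treated at an MTD confirmed in 6

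*Combined protocol and SAP*

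**What the plan says.** **Phase I.** Section 14.1 (Biostatistics) defines the MTD as the "highest dose level with an observed incidence of DLT in no more than one out of six patients" treated at a level. Section 11.5 (Establishment of Maximum Tolerated Dose) defines it as "the dose level below that which produces Grade III/IV non-hematologic toxicity in" 33% or more of patients. The two agree on the count: 2 of 6 is 33%. Section 9.0 also ends the study if the lowest tretinoin level is not tolerated.

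**Phase II.** Section 14.1 continues: "At the end of this study, the phase II component of the trial will begin at the MTD determined", and "The six patients treated at the MTD will be included as part of the phase II component of the trial". Accrual stops if there are 2 or fewer responses in 27. The combination is judged worthy of further study on 7 or more responses in 40. On toxicity, the section says only: "Frequencies of toxicities based on the NCI Common Toxicity Criteria version 2.0 will be tabulated".

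**What continues throughout.** Grade III or IV non-hematologic toxicity attributable to either drug interrupts that patient's treatment and leads to a dose reduction on resumption (Section 9.0). Slow recovery removes the patient (Section 13.3). SAEs are reported to the IRB/PB within 5 calendar days (Section 17.3). Section 16.3 places phase I and II trials under an institutional Data and Safety Monitoring Committee (DSMC) and says "the monitoring procedures will be established at the time of protocol activation". It gives no threshold, count or review interval for this trial.

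**The concern.** The stated objective (Section 1.0) covers safety as well as efficacy. Six patients say little about a DLT rate, and most patients treated at the chosen dose come after those six. If the six were unrepresentative, the first 12, 18 or 27 patients would show it. As the plan is written, however, no such count obliges anyone to pause accrual and look. What is at stake is how many patients are treated at a dose that the phase I criterion would have rejected, and how soon that is noticed.

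**Working it through.** **Inputs.** From Section 14.1: at most 1 DLT in 6 for the MTD; 6 patients carried over; "a maximum of 40 patients will be accrued to the phase II component of this trial"; stage 1 of 27. From Section 11.5: 33% or more is above the MTD. The documents give no expected DLT rate for the combination, so the true rates p below are assumptions, shown as a range.

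**1. The plan's own figures.** The escalation probability is (1−p)³ + 3p(1−p)²·(1−p)³. At p = 0.10 to 0.60 this gives 0.906, 0.709, 0.494, 0.309, 0.172 and 0.082, matching the stated .91, .71, .49, .31, .17 and .08. The two-stage response design (2/27, 6/40) has exact type I error 0.0977 and power 0.9001, as stated. Neither is in dispute.

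**2. Patients exposed after phase I.** 40 − 6 = 34 in all, of whom 27 − 6 = 21 come before the response stop.

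**3. What six patients establish.** Exact one-sided 95% upper limits for the DLT rate are 39% after 0 of 6 and 58% after 1 of 6. Even a clean cohort does not exclude 33%.

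**4. Chance that a level tested in 6 is accepted.** P(X ≤ 1) = (1−p)⁶ + 6p(1−p)⁵. At p = 1/3 this is 0.0878 + 0.2634 = 0.351.

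| True DLT rate | P(at most 1 of 6) | Expected DLTs in 34 (34p) |
|---|---|---|
| 20% | 0.66 | 6.8 |
| 33% | 0.35 | 11.3 |
| 40% | 0.23 | 13.6 |
| 50% | 0.11 | 17.0 |

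The last column assumes that all 34 accrue, which requires at least 3 responses in the first 27.

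**5. Applying the phase I criterion cumulatively.** One third of 12, 18 and 27 is 4, 6 and 9. The calculation is an exact recursion from patient 7, given at most 1 DLT in the first 6. At p = 1/3 the starting weights are 0.0878/0.3512 = 0.25 for 0 DLTs and 0.75 for 1 DLT. The chance of reaching 4 by patient 12 is 0.25 × P(4 or more of 6) + 0.75 × P(3 or more of 6) = 0.25 × 0.100 + 0.75 × 0.320 = 0.265. First crossings at 18 and 27 add 0.127 and 0.096, for a total of 0.488.

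| True DLT rate | 15% | 20% | 25% | 30% | 33% | 40% | 50% |
|---|---|---|---|---|---|---|---|
| P(pause), three looks | 0.04 | 0.10 | 0.21 | 0.37 | 0.49 | 0.71 | 0.92 |
| P(toxicity-triggered pause), as written | 0 | 0 | 0 | 0 | 0 | 0 | 0 |

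**6. Why the count should not enter the success rule.** Suppose a positive result also required that no boundary was crossed, and that DLT and response are independent. Power at a 25% response rate would be 0.9001 × (1 − P(pause)): 0.9001 × 0.964 = 0.87 at a DLT rate of 15%, 0.9001 × 0.899 = 0.81 at 20%, and 0.9001 × 0.786 = 0.71 at 25%. The plan promises at least 0.90, and the design has no slack.

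**The case against.** A reader might infer that toxicity stops governing the trial after phase I, or that phase II can succeed however toxic the regimen proves. The documents do not support either reading. Patient-level interruption, dose reduction and removal continue, and each SAE report must say whether an amendment is needed. Death during treatment counts as Failure (Section 12.5), and a patient removed early loses the chance to respond, so severe toxicity weighs indirectly on the 7-of-40 rule.

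Three further objections have force. Section 16.3 refers to monitoring procedures held outside this document, so the fair statement is that no threshold is stated here, not that none exists. The 33% figure was written to choose a phase I dose level and is never applied to phase II; using it there is an extension, though it is the only toxicity ceiling in the documents. And DLT is not worded in one way: Section 11.5 ties cohort expansion to attribution to tretinoin, while Section 14.1 counts any grade 3–4 non-hematologic toxicity in cycle 1.

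What still stands is that the continuing rules act on one patient or one event at a time. None of them turns an accumulating DLT count into a decision about accrual.

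**Conclusion.** The concern holds as a gap in trial-level monitoring. It is a design weakness that should be repaired; no stated figure is wrong and no passage is contradicted by it. A dose at the protocol's own 33% limit passes the six-patient test about one time in three, and up to 34 more patients may then be treated with no stated count that prompts a review. The probabilities are exact binomial and rest on assumed true DLT rates, on independence between patients, and, for the 11, 14 or 17 expected DLTs, on full accrual. They apply to a level once it is tested in 6. They do not show that the dose chosen is likely to be this toxic. The gap also extends beyond these figures: DLTs are counted in cycle 1 only (Section 14.1), while treatment may run to 10 cycles (Section 9.0).

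**What to change.** 1. Reconcile the DLT wording in Sections 11.5 and 14.1 on whether attribution to tretinoin is required. No count can be applied until that is settled.
2. Add to Section 14: cycle-1 DLTs at the phase II dose are counted cumulatively, including the 6 carried-over patients. If 4 or more of the first 12, 6 or more of the first 18, or 9 or more of the first 27 have a DLT, accrual pauses and the DSMC decides whether it continues.
3. State whether accrual continues while the last patients at each look complete cycle 1. With 3–4 patients accrued per month and a 28-day cycle, the choice is a hold of about a month or an overrun of about 3–4 patients per look.
4. Leave the 7-of-40 rule unchanged. A toxicity condition there would cost power and would bar a positive result even where the DSMC had allowed the trial to continue. Report the observed DLT rate at the phase II dose, with an exact confidence interval, beside the response result.

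**Cost.** One paragraph and three counts of adverse-event data already collected; no extra patients or visits. The price is a possible unneeded pause: probability 0.04, 0.10, 0.21 and 0.37 at true rates of 15%, 20%, 25% and 30%, all below the criterion. A pause leads to review, not automatic closure.

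**Limits.** At a true 33% the rule triggers only about half the time. It does not cover the last 40 − 27 = 13 patients or toxicity after cycle 1.
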